## 5 STUDY EVALUATIONS AND MEASUREMENTS

### 5.1 Screening and Monitoring Evaluations and Measurements

#### 5.1.1 Medical Record Review

Information from the medical record will be recorded and used for this study. This information will include medical history, information about your condition, lab and radiology results, medications, treatments, vital signs, and the response to treatments. We will be reviewing the medical record throughout the study.

We plan to follow-up all subjects for 3 days post-intervention in all study phases. It is possible that some study subjects might be discharged from the hospital prior to this endpoint. In such instances, we will need to contact the parent/guardian of the subject (as third party and not part of research procedures) and administer the follow-up questionnaire on a daily basis (till post-intervention day 3). As we cannot predict which subject is likely to be discharged prior to 3 days, we will obtain contact information for parents/guardians of all subjects at the time of obtaining informed consent.

Variables that will be abstracted from the EHR will include the following.

- Basic demographic information including subject name, medical record number (MRN), account number (CSN), Date of birth (DOB), race, ethnicity, sex, age at time of Study Intervention, weight, stature, calculated BMI, location (PICU/PCU/IR) and dates of hospitalization (length of stay)
- Contact information of parent/guardian will be collected to follow-up subjects for study related events, (in case subject is discharged prior to post-intervention day 3)
- Type of EAD(P)
- Date and place of EAD(P) insertion
- Length of EAD(P)
- EAD clog information
- Medications
- Nutrition
- Diagnoses
- Procedures
- Severity of illness
- Ventilator parameters (if applicable)
- Medications administered through EAD(P) preceding clog

- Nutrition administered through EAD(P) preceding clog
- Past Medical History
- Past Surgical History
- Established age-appropriate pain scales
- Laboratory results and radiology results

### **5.1.2 Physical Examination**

Confirmation of EAD(P) occlusion will be made by CHOP staff according to CHOP protocol.

Documentation of Subject's clinical status (i.e., abdominal exam for contour, symmetry, etc.) will be reviewed and/or assessed by Investigator.

### **5.1.3 Vital Signs**

Vital signs will be collected both as part of routine clinical care (baseline and daily follow-up) and research procedures (before, during and after the study interventions). Baseline vital signs and daily follow-up vital signs will be extracted from the EHR (EPIC).

### **5.1.4 Laboratory Evaluations**

None.

### **5.1.5 Pregnancy Testing**

Prior to being enrolled in the study, a urine/blood pregnancy test will be performed for female Subjects  $\geq$  10 years of age OR females who have experienced the onset of menses.

### **5.1.6 Other Evaluations, Measures**

Portable abdominal radiograph with contrast agent after intervention (and portable abdominal radiograph, prior to intervention, if needed).

Clinical Patient Assessment Measurements (i.e., pain, feeding tolerance, and usual measures to determine EAD(P) location) will be performed prior to, immediately following, and for up to three (3) days after all interventions. Patients who are discharged from the hospital prior to three days will be followed up daily by phone for Clinical Assessment Measurements i.e., pain, feeding tolerance and EAD(P) location as assessed by caregiver until post intervention day three.

Age Appropriate Pain Scale Assessments (these scales include, but are not limited to): Face, Legs, Activity, Cry, Consolability (FLACC) Scale; Revised Face, Legs, Activity, Cry, Consolability (rFLACC) Scale; FACES Pain Scale revised (FPS-R); Numeric Pain Scale; Nursing judgment

Behavioral Likert scale and Generic Behavioral Analysis developed in conjunction with The Food and Drug Administration (FDA) will be used to assess subject behaviors during the study intervention. The Behavioral Likert Scale will be used by the study investigators to objectively assess subject behavior, while the Generic behavioral Analysis consists of questions that will be administered by the study investigators to the subject and their parent/guardian to assess their subjective assessment of the study intervention.

EAD(P) air and water flush.

## **5.2 Efficacy Evaluations**

Efficacy (i.e. patency restoration) will be measured by the ability to flush the EAD(P) with 10 ml of air within five (5) minutes following the intervention by the investigator.

### **5.2.1 Diagnostic Tests, Scales, Measures, etc.**

With the exception of abdominal radiographs as described, and the pain, stress and behavioral scales used, there are no other diagnostic tests, scales, or measures used for this Study.

## **5.3 Pharmacokinetic Evaluation**

There is no pharmacokinetic evaluation for this Study.

## **5.4 Safety Evaluation**

The FDA has deemed TubeClear® to be non-significant risk for use in this study (**Appendix D**). Following successful restoration of EAD(P), a portable abdominal radiograph with contrast agent will be obtained. A radiologist (blinded to the study) will assess the radiographs for adverse events related to the respective Intervention and report results.

Subjects will be monitored for the occurrence of adverse events defined as any untoward or unfavorable occurrence. A description of all events will be recorded in the Study database.

Anticipated adverse events (AE), or “TubeClear® Specified Events” include: EAD displacement, EAD perforation and enteral tract tissue injury.

The relationship of each event to the study protocol will be classified according to severity, expectedness and relatedness by the bedside clinicians and recorded.

Unanticipated Problems (UP) involving risk to Subjects or others will also be tracked. UP includes any incident, experience, or outcome that is unexpected, related or possibly related to Intervention, and suggests that research places Subjects or others at greater risk for harm.

An AE is a reportable Serious Adverse Event (SAE) if it is serious, unexpected and related or possibly related to the Intervention.

**Expedited** reporting timeline for all SAE and unanticipated problems related to the Intervention or from protocol violations:

- a. Principal Investigator or designee will notify their local IRB, medical monitor and AMI **within 24 hours of the event.**

A full narrative report describing the event within 7 calendar days will be submitted to the local IRB, medical monitor and AMI. Such reports will include a detailed description of the SAE/UP, an explanation of the basis for determining that the event represents a SAE/UP, and a description of any corrective actions that are proposed in response to the SAE/UP.

## 6 STATISTICAL CONSIDERATIONS

### 6.1 Primary Objective

The primary objectives of this study are to 1) evaluate feasibility and tolerability of TubeClear® to restore patency in occluded EAD(P)s, and 2) compare efficacy of TubeClear® to the CHOP Standard Treatment to restore patency in occluded EAD(P)s.

The primary endpoints in Phase I are feasibility and tolerability of TubeClear® intervention. Feasibility will be defined as ability of the user to operate TubeClear® device (as per instructions and training in **Appendix F**) from insertion of the clearing stem into the occluded EAD(P) through device activation to patency restoration. Tolerability will be defined as ability of the Subject to undergo TubeClear® intervention.

The primary endpoint in Phase IIA is the ability of TubeClear® intervention to restore patency in Subjects with occluded EAD(P)s. This will be termed as EAD(P) patency restoration and will be measured by the ability to flush the EAD(P) with 10 ml of air within five (5) minutes after completion of the intervention.

The primary endpoint of Phase IIB is the efficacy of TubeClear® intervention compared to CHOP Standard Treatment to restore patency in Subjects with occluded EAD(P)s. EAD(P) patency restoration will be measured by the ability to flush the EAD(P) with 10 ml of air within five (5) minutes after completion of either intervention.

### 6.2 Secondary Objectives (or Aim)

The secondary objectives of this study are to assess subject pain, changes in physiological parameters, distress related EAD(P) events and adverse events related to the interventions.

In Phase I, Subject pain will be assessed before and after use of TubeClear® intervention using established age-appropriate pain scales. Acute changes in physiologic parameters will be measured, including changes in heart rate, blood pressure and respiratory rate. Distress related EAD(P) events which may be manifested by pulling or yanking of the EAD(P) will be monitored in relation to intervention. Following the TubeClear® intervention, each Subject will receive an abdominal radiograph with contrast. Study procedures carried out in IR may utilize low-dose fluoroscopy as an alternative to the portable abdominal radiograph. Radiographs will be reviewed by a radiologist (blinded to the study) for EAD(P) adverse events (i.e., EAD(P) displacement, EAD(P) damage, enteral tract tissue injury) attributable to the TubeClear® intervention.

In Phase IIA, Subject pain will be assessed before and after use of TubeClear® intervention using established age-appropriate pain scales. Acute changes in physiologic parameters will be measured, including changes in heart rate, blood pressure and respiratory rate. Distress related EAD(P) events which may be manifested by pulling or yanking of the EAD(P) will be monitored in relation to intervention. Following the TubeClear® intervention, each Subject will receive an abdominal radiograph with contrast. Study procedures carried out in IR may utilize low-dose fluoroscopy as an alternative to the portable abdominal radiograph. Radiographs will be reviewed by a radiologist (blinded to the study) for EAD(P) adverse

events (i.e., EAD(P) displacement, EAD(P) damage, enteral tract tissue injury) attributable to the TubeClear® intervention.

In Phase IIB, Subject pain will be assessed before and after use of either intervention using established age-appropriate pain scales. Acute changes in physiologic parameters will be measured, including changes in heart rate, blood pressure and respiratory rate. Distress related EAD(P) events which may be manifested by pulling or yanking of the EAD(P) will be monitored in relation to either intervention. Following either intervention, each Subject will receive an abdominal radiograph with contrast. Study procedures carried out in IR may utilize low-dose fluoroscopy as an alternative to the portable abdominal radiograph. Radiographs will be reviewed by a radiologist (blinded to the study) for EAD(P) adverse events (i.e., EAD(P) displacement, EAD(P) damage, enteral tract tissue injury) attributable to either intervention. Incidence of adverse events attributable to the intervention (i.e. EAD displacement, EAD damage, enteral tract tissue injury) following the intervention will be monitored and reported in both groups.

In all phases, surveillance will include daily assessment for adverse events related to the respective study intervention (i.e. subject pain, feeding intolerance, EAD(P) displacement, EAD(P) damage, enteral tract tissue injury) and will continue for three (3) days. Patients who are discharged from the hospital prior to 3 days will be followed up daily by phone until completion of 3 days following study interventions.

1. Intervention time (measured in minutes) is the time interval between commencement of intervention and achievement of EAD(P) patency (if successful).
2. Physiological parameters will be recorded from the Subject's EHR.
3. Distress related EAD(P) events which may be manifested by pulling or yanking of the EAD(P) will be monitored and recorded by Research Personnel or the Subject's nurse.

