#### In-vitro Animal Testing

Safety was evaluated in an over-insertion mode (contrary to the Instructions for use) in an *in-vitro* animal model. For normal operation, a depth control collar limits the insertion of the Clearing Stem into the EAD; thus prevents the Clearing Stem tip from exiting the EAD. To test safety, *ex-vivo* porcine stomach and small intestine tissue samples with thicknesses similar to humans of age 0 to 39 years of age were examined in the simulated over-insertion mode. A porcine model was selected due to similarity of gastric features to that of humans aged 0 to 39 years. The range of intestinal thickness (jejunum) for human ages 0 to 39 years is 0.6 – 1.0 mm (**Table 3**). Tissue samples from the porcine intestine tissue used for testing were between 0.284 mm and 1.0 mm as measured via two independent methodologies.

As such, it was concluded that the tissue samples used for this safety testing were representative of both adult and pediatric patients and the results of the testing are applicable to both populations (**TR-4010-022**).

The EAD(A) Clearing Stem was advanced at a rate of 65-70 mm/min to simulate actual use. The maximum force of the Clearing Stem tip on the tissue sample was 3.597 N. The advancement of the Clearing Stem stopped when the wire was observed to be bent at approximately 45°. In the 60 trials run, the Clearing Stem caused small indentations, but no full puncture was observed (**TP-4010-008**, and **TR-4010-008**).

This testing was repeated for the EAD(P) Clearing Stem design. Tissue samples from the porcine intestine (jejunum) tissue were on average between 0.62 mm and 0.92 mm. It was concluded through statistical analysis that this was representative of both adult and pediatric patients and the results of the testing are applicable to both populations. No punctures of porcine intestine (jejunum) tissue samples were achieved in a realistic worst-case misuse test scenario (**TP-4021-020** and **TR-4021-020**).

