#### In-vivo Animal Testing

The safety and efficacy of the Alpha (first design iteration) EAD(P) TubeClear® Clearing Stem design was tested in a live porcine model at the Medical University of South Carolina. Use of TubeClear® was performed in a porcine model to simulate pediatric insertion by [name], VMD, a veterinarian, [name], FACG, CNSP, AGAF, FASGE, a gastroenterologist, conducted the standard Intervention and [name], DVM, Ph.D., a board certified pathologist, conducted the pathology evaluations.

1) The efficacy of the EAD(P) Clearing Stem in clearing EAD(P)s with simulated occlusions was evaluated in a porcine model. Patency was restored in an average time of 2.37 minutes (**TP-5017-009**, **TR-5017-009** and **TR-5017-010**).

2) Safety was evaluated in an over-insertion mode (contrary to the Instructions for use). For normal operation, a depth control collar limits the insertion of the Clearing Stem into the EAD; thus prevents the Clearing Stem tip from exiting the EAD. To test safety, the collar was removed, and the Clearing Stem's distal tip was intentionally advanced approximately 2.5cm beyond the distal end of the EAD(P) so that the distal tip contacted and remained in contact with the porcine mucosal intestinal tissue for six (6) minutes while in 'on mode' (**TP-4010-008**, and **TR-4010-008**). No evidence suggested TubeClear® (consistent to instructions for use) produced intestinal trauma beyond that which can be caused by insertion of an EAD(P). In the over-insertion situation (inconsistent to instructions for use), the Clearing Stem caused lesions that were highly localized, but no full puncture was observed.

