In Phase IIB, subjects will be randomized into either TubeClear® intervention or CHOP Standard Treatment using a predetermined computer generated randomization sequence stored in opaque sealed envelopes. Prior to the intervention, the location of the EAD(P) will be determined based on review of radiographs. The Investigator may obtain a new radiograph if the EAD(P) location is uncertain. The Investigator will determine the length and diameter of the EAD(P) from the EHR and/or the length marking (in cm) at the exit point of the EAD(P) from the body surface orifice. If randomized to TubeClear®, the Operator-set Collar on the clearing stem of TubeClear® will be placed corresponding to the EAD(P) measured length recorded by the Investigator. The TubeClear® Instructions for Use (i.e., Operator's Manual) will be followed by the user to restore patency to the EAD(P). If randomized to CHOP Standard Treatment, the CHOP protocol to restore patency to occluded EAD(P) will be followed. EAD(P) patency restoration will be measured by the ability to flush the EAD(P) with 10 ml of air within five (5) minutes after completion of the intervention. After successful air flushing, aspirate will be extracted through the EAD(P), and the pH of the contents checked to confirm location according to CHOP standard of care. Following confirmation of correct EAD(P) placement, 5-20 ml of water will be flushed through the EAD to assure continued patency. Following either intervention, the Subject will receive an abdominal radiograph with contrast. A radiologist (blinded to the study) will assess the radiographs for adverse events (i.e., EAD(P) displacement, EAD(P) damage, enteral tract tissue injury) attributable to the intervention. If either intervention is unable to restore EAD(P) patency, further steps to restore patency of the occluded EAD will be determined by the clinical team per usual practice.

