### **6.3.6 Safety Analysis**

All Subjects entering the Study will be included in the safety analysis. Clinical Patient Assessment Measurements (i.e., pain, feeding tolerance, and usual measures to determine EAD(P) location) will be performed prior to, immediately following, and for up to three (3) days after all Interventions. Clinically significant changes will be addressed and managed by the Subject's medical team, but recorded, reported, and followed by the Study team. Surveillance will include assessment for any adverse event(s) related to the intervention (i.e. EAD(P) displacement, EAD(P) damage, enteral tract tissue injury) and will continue for up to three (3) days following interventions in either group. Patients who are discharged from the hospital prior to three days will be followed up daily by phone for Clinical Assessment Measurements i.e., pain, feeding tolerance and EAD(P) location as assessed by caregiver until post intervention day three.

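### Tissue injury is a safety endpoint, but its only named test is not shown to detect non-perforating lesions, and the Phase IIB comparison counts only perforation

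*Combined protocol and SAP*

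**What the plan says.** **The test.** Section 6.2 assigns tissue injury to the film in all phases: "Radiographs will be reviewed by a radiologist (blinded to the study) for EAD(P) adverse events (i.e., EAD(P) displacement, EAD(P) damage, enteral tract tissue injury"). It adds that "Study procedures carried out in IR may utilize low-dose fluoroscopy as an alternative to the portable abdominal radiograph". Section 5.2.1 says no diagnostic test is used beyond the radiographs and the pain, stress and behavioral scales. Tissue injury is given no definition, grading or reading criteria.

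**The clinical checks.** Section 6.2 also provides three days of daily surveillance that names tissue injury. What is measured is set out in 6.3.6: "Clinical Patient Assessment Measurements (i.e., pain, feeding tolerance, and usual measures to determine EAD(P) location) will be performed" before, just after, and for up to three days after the intervention. Table 1 schedules an examination on Days 1 to 3, and 5.1.2 describes it by abdominal contour, symmetry and the like. After early discharge, the daily call in 4.3 covers pain, feeding tolerance and tube location.

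**The comparison.** In Phase IIB, 6.3.4 item 5 compares the proportions with tube displacement, tube damage and tissue perforation.

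**The preclinical findings (1.3.1).** In vitro, with the adult stem in an over-insertion mode, "the Clearing Stem caused small indentations, but no full puncture was observed" over 60 trials. In live animals, also over-inserted, "the Clearing Stem caused lesions that were highly localized, but no full puncture was observed". In that work "a board certified pathologist, conducted the pathology evaluations"; no imaging of the lesions is described.

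**Who is examined.** Section 6.2 gives the film to each Subject, whereas 5.4 describes it after successful restoration. After a successful air flush, under 3.1.2, "aspirate will be extracted through the EAD(P), and the pH of the contents checked".

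**The concern.** The endpoint is called tissue injury, but the plan narrows it twice. The only test aimed at it is a contrast film with no stated ability to show a lesion that has not gone through the wall. The only formal comparison then counts perforation. The kind of injury that the sponsor's own testing produced falls between the two.

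This matters because of how a zero would be used. Phase I adverse events go to the IRB, which decides whether Phases IIA and IIB proceed (3.1, 6.5). Phase IIA enrols children under 11, and Table 3 lists the thinnest jejunum at ages 0 to 4. Section 9.5 says the data may support a 510(k) submission. In either setting, a count of no tissue injury could be read as evidence that the device does not injure tissue, which is more than these measurements can show.

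**Working it through.** **1. The plan's own figure.** The documents give no expected rate of tissue injury and no sensitivity for the film. The only sample-size figure, 17 per arm, is for efficacy (95% versus 50%, alpha 0.05, power at least 0.80; section 6.4). It reproduces: two-sided Fisher exact power is 0.777 at 16 per arm and 0.813 at 17. It has no bearing on injury.

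**2. The sections side by side.**

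| Step | Section | Content |
|---|---|---|
| Endpoint | 6.2 | tissue injury |
| Named test | 6.2, 5.2.1 | contrast film, or fluoroscopy in IR |
| Listed clinical measurements | 6.3.6, 4.3 | pain, feeding tolerance, tube location |
| Named hazard | 8.1 | stem leaves the tube and punctures the mucosa |
| Phase IIB comparison | 6.3.4 item 5 | perforation |

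No row prompts for a sign of non-perforating injury. Read literally, item 5 would not count such an injury even if surveillance found it.

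**3. The chance of seeing none.** Let *p* be the true rate of non-penetrating lesions, *s* the chance that a child with one is recorded as injured (for the film alone, its sensitivity), and *n* the number of TubeClear enrolments, 15 + 15 + 17 = 47. Both *p* and *s* are assumptions. Enrolments are treated as independent, although a child may be enrolled up to three times.

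P(none detected) = (1 − *p* × *s*)^*n*. For example, at *p* = 0.10 and *s* = 0.25: (1 − 0.025)^47 = 0.30.

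| *s* | *p* = 5% | *p* = 10% | *p* = 20% |
|---|---|---|---|
| 1 | 0.09 | 0.007 | <0.001 |
| 0.5 | 0.30 | 0.09 | 0.007 |
| 0.25 | 0.55 | 0.30 | 0.09 |
| 0.10 | 0.79 | 0.62 | 0.39 |
| 0 | 1.0 | 1.0 | 1.0 |

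**4. What a zero would bound.** The exact two-sided 95% upper limit after no events is 1 − 0.025^(1/*n*): 7.5% for 0/47 and 19.5% for 0/17. These limits apply to *detected* injury. Dividing by *s* gives the limit for the true rate. For 0/47 that is 0.075/0.5 = 15%, 0.0755/0.25 = 30%, and 0.0755/0.10 = about 75%. At *s* = 0 there is no limit. In that case the nominal 7.5% would lie below a true rate of 10%, though it would cover one of 5%.

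**5. Observations that depend on success.** At the planned efficacy rates, an aspirate would be available in about 0.95 × 17 = 16 TubeClear children and 0.50 × 17 = 8.5 controls. The same imbalance would apply to the film if 5.4 were followed instead of 6.2.

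**The case against.** A reader might infer that the trial will report zero tissue injury whatever the device does. The documents do not support that.

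- The argument about non-penetrating lesions does not extend to a full perforation, which is the hazard that 8.1 names.
- Sections 6.2 and 6.3.6 provide three days of surveillance that names tissue injury. Sections 5.4 and 8.1 make any untoward occurrence recordable, so a new bleed would be an adverse event. What is missing is a prompt for it and a route into the injury result.
- Section 6.2 says the incidence of tissue injury will be reported in both Phase IIB groups, and Phases I and IIA report adverse events descriptively. The restriction to perforation lies in the Phase IIB test.
- Zero is certain only if detection is nil by every route. The table in the working shows how strongly the result depends on sensitivity, which nobody has stated.

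A reader might also infer that ordinary use of the device causes lesions. The live-animal lesions came from a first-iteration stem with the collar removed and the tip held about 2.5 cm beyond the tube for six minutes. The in-vitro indentations came from the adult stem. For use per instructions, 1.3.1 reports no evidence of trauma beyond what tube insertion can cause. Over-insertion remains relevant because 1.3.1 itself says the operator-set collar carries a potential for operator error.

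Finally, the documents do not say that the localised lesions bled, so bleeding has no more demonstrated sensitivity for them than the film has. That stands, and it limits what the remedy can claim. The CRF and the follow-up questionnaire are not reproduced. They may already ask about bleeding, but the call content in 4.3 does not mention it.

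**Conclusion.** The point holds as a matter of endpoint definition and interpretation. Non-perforating tissue injury lies within the stated endpoint, is not prompted for in any listed check, has no test shown to detect it, and is outside the Phase IIB comparison. A zero would support only that no injury was apparent on film or clinically.

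The size cannot be fixed from the documents. If lesions occurred in 10% of 47 TubeClear enrolments, finding none would be unlikely at sensitivity 0.5 (0.09) but more likely than not at 0.10 (0.62). Both the lesion rate and the sensitivity are assumptions, and low film sensitivity for superficial lesions is a clinical inference. The conclusion about item 5 needs neither assumption, because it follows from the wording.

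**What to change.** In 6.2 and 6.3.4 item 5, replace perforation with tissue injury reported in two separate parts, the same in both arms:

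- (a) perforation or contrast leak on the blinded film;
- (b) clinically apparent injury from the day 0 to 3 surveillance, with new gastrointestinal bleeding as a prompted item at each daily assessment and phone call.

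Tabulate both parts for Phases I and IIA as well. Give exact upper confidence limits for zero counts, and word the conclusion as no radiographically or clinically apparent injury. If visible blood in the pH aspirate is noted, report it separately and do not compare it between arms, because the aspirate is drawn only after a successful flush. Reconcile 5.4 with 6.2 on who receives the film, so that the denominator of (a) is clear.

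The cost is one prompted CRF item (two if aspirate blood is noted) and wording, with no new procedure or reader. The downside is that bleeding is not specific to the intervention and may miss superficial lesions. It should therefore count only if new and be kept apart from the film result.
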